PROTOCOL TITLE: Comparison of two high-intensity gait training interventions on contraversive pushing behaviors in individuals poststroke

PRINCIPAL INVESTIGATOR (PI):

[name] Department of Physical Medicine and Rehabilitation Northwestern University Shirley Ryan AbilityLab [name] [name] [name] [contact]

VERSION DATE:

07/17/2020 (V01)

STUDY SUMMARY:

Investigational Agent(s)	N/A
(Drugs or Devices)	
IND / IDE / HDE #	N/A
Indicate Special Population(s)	 Children Children who are wards of the state Adults Unable to Consent Cognitively Impaired Adults Neonates of Uncertain Viability Pregnant Women Prisoners (or other detained/paroled individuals) Students/Employees
Sample Size	30 participants
Funding Source	Shirley Ryan AbilityLab: Brown Fellowship Grant
Indicate the type of consent to be obtained	Written Verbal/Waiver of Documentation of Informed Consent Waiver of HIPAA Authorization Waiver/Alteration of Consent Process
Site	 Lead Site (For A Multiple Site Research Study) Data Coordinating Center (DCC)
Research Related	Yes
Radiation Exposure	🖾 No
DSMB / DMC / IDMC	☐Yes ⊠No

OBJECTIVES

The purpose of this study is to investigate the effect of two high-intensity gait training interventions on contraversive pushing behaviors (CPB) in individuals poststroke in the acute inpatient rehabilitation setting. We will also evaluate the effect of these interventions on functional mobility, strength, balance, and endurance. Furthermore, we intend to measure therapist burden when mobilizing individuals with CPB.

BACKGROUND

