There is little research on the utilization of overground-based robotic exoskeletons like the EksoNR to train and ambulate individuals with acute and chronic stroke diagnoses. In addition, high quality evidence guiding physical therapy intervention, specifically gait training, in individuals with CPB is scarce. Robotic assisted gait training utilizing the Lokomat system over a treadmill has been effective in reducing CPB.^{4,6,7} However, no studies have assessed the efficacy of gait training with an exoskeleton robotic suit overground as we are proposing to do. Traditional therapeutic interventions in individuals with CPB typically consists of progressing functional mobility while orienting to midline with various forms of visual and tactile feedback.^{4,5,8-13} It is hypothesized that the EksoNR will be an efficacious intervention for this population because of its ability to position and orient an individual to midline while simultaneously working on gait training and decreasing the physical burden on clinicians. Unquestionably, there is a demand for research to support appropriate interventions, guide best physical therapy practice, and promote ways to safely maximize high-intensity gait training within this specific population.

This study will include two interventional groups. Intervention for group one will consist of bodyweight-supported treadmill training + overground gait training. Intervention for group two will consist of gait training in the EksoNR exoskeleton + overground gait training. We will enroll 5-10 participants in each intervention group with the goal of 10 participants completing the study.

IRB Project #: STU00213155, Medical Clearance Form (v01) 08/05/2020Page 2 of 17Principal Investigator: [name], PT, PhDHRP-593 / v03152019

Since participants are inpatients on an acute rehabilitation unit, they will simultaneously be receiving intensive physical, occupational, and speech therapies outside of our research study as part of the standard of care at Shirley Ryan AbilityLab.

Intervention Delivery Systems:

Woodway PPS Medical Series + Body Weight Support LokoStation 55/70

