- 14. Borg Rating of Perceived Exertion (RPE): The Borg RPE is a tool to measure the subjective report of effort, exertion, and fatigue during physical work. It consists of a 15-point scale from 6-20, in which 6=no exertion and 20=absolute maximum exertion. It is presented to the participant in written format with descriptors to standardize the report of perceived exertion across tasks.
- **15.** Numerical Rating Pain Scale (NPRS): The NPRS is used to measure the subjective report of pain intensity. It consists of an 11-point scale, 0-10, in which zero indicates no pain and ten indicates the most intense pain imaginable. In this study, therapists will be provided a written format of the NPRS to report their perceived pain following delivery of each intervention session.

IRB Project #: STU00213155, Medical Clearance Form (v01) 08/05/2020Page 7 of 17Principal Investigator: [name], PT, PhDHRP-593 / v03152019

DATA COLLECTION AND ANALYSIS

Data from participants will be collected during their hospital stay, including clinical and functional outcomes. The complete medical history of the participants, including physical findings, radiological reports such lesion size, location, type, medications, intervention training parameters and therapist-assessed clinical outcomes may also be collected (See Clinical Assessments section). Participants' records and data will be kept confidential and in compliance with HIPAA requirements. Research data will be de-identified and stored in locked cabinets in the lab with access only to research staff. Electronic data will be de-identified and kept on secure, password protected files, and password protected computers. Analysis will be completed to compare the two intervention groups and draw conclusions on the efficacies of both interventions.

Photographs, audio, and video recordings:

We may photograph, audio, or video record the participants during the study to be used for scientific publications and scholarly presentations only. The photographs will be de-identified, meaning that the face of the participants will not be shown. Participants will be given the choice to accept or decline this optional aspect during the informed consent process. Their choice will not impact their participation in the study.

STUDY TIMELINES

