We anticipate it will take each participant up to eight weeks to complete the study protocol. Clinical assessments will be performed at baseline and once weekly for up to eight assessment sessions or until the participant is discharged. The intervention will be delivered three times weekly up to 24 sessions or until the participant is discharged. In total, each individual will participate in 13-34 sessions [Refer to Figure 3]. We anticipate a 12-month period to enroll all inpatient participants.

Type of Session	# of Sessions	Time Required for Each Session
Enrollment/ Baseline Clinical Assessment/ Baseline Measurements	1-2	60-120 minutes
Weekly Clinical Assessments	3-8	60-90 minutes
Training Protocol	9-24	60-90 minutes

Figure 3. Summary of sessions.

INCLUSION AND EXCLUSION CRITERIA Inclusion Criteria:

- Age 18-80 years old
- Unilateral, supratentorial ischemic or hemorrhagic stroke within the past six months
- Medical clearance from primary medical team (signed Medical Clearance form)
- CPB as determined by a score of >0 on the Scale for Contraversive Pushing
- Adequate cognitive function as determined by the NIH scale: score ≤1 on question 1b and score =0 on question 1c
- Informed consent provided by participant or POA
- English speaking

Exclusion Criteria:

- Severe aphasia limiting ability to express needs or discomfort verbally or nonverbally
- Severe behavioral neglect as determined by a score of ≥ 21 on Catherine Bergego Scale (CBS) via the Kessler Foundation-Neglect Assessment Process (KF-NAP)¹⁶
- History of prior stroke
- Concurrent neurologic condition (i.e PD, TBI, MS, etc.)
- History of peripheral nerve injury
- Joint contracture or significant spasticity in the lower limbs (Modified Ashworth Scale \geq 3)
- Severe knee, hip, or ankle osteoarthritis
- Severe osteoporosis as indicated by physician medical clearance
- Open wounds on surfaces in contact with exoskeleton or harness
- Unstable spine or unhealed fractures
- Weight bearing precautions
- Unresolved deep vein thrombosis (DVT)
- Concurrent participation in other lower limb research studies that according to the PI is likely to affect study outcome or confound results
- Pregnancy

EksoNR Exclusion Criteria¹⁷:

- Weight >220 lbs (100 kg)
- Height below 60 inches or above 76 inches
- Standing hip width of approximately 18 inches or more
- Joint contractures or range of motion deficits that limit normal range of motion during ambulation
 - Knee flexion contracture greater than 12°

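### The protocol promises conclusions on the efficacy of each intervention, but with two active arms on top of usual therapy and no control, neither arm's own improvement can be attributed to its intervention without untestable assumptions

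*Protocol*

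**What the plan says.** Data Collection and Analysis holds the protocol's one statement of what the analysis will conclude: "Analysis will be completed to compare the two intervention groups and draw conclusions on the efficacies of both interventions". It names a comparison of the groups and, joined by a conjunction, conclusions on the efficacy of each intervention.

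Two other places point the same way. The Objectives set out to "investigate the effect of two high-intensity gait training interventions on contraversive pushing behaviors (CPB) in individuals poststroke". The Background states: "It is hypothesized that the EksoNR will be an efficacious intervention for this population", and names no comparator.

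The design is described mainly in the Background. "This study will include two interventional groups": treadmill training with body-weight support plus overground gait training, and EksoNR training plus overground gait training. Of all participants it says that "they will simultaneously be receiving intensive physical, occupational, and speech therapies outside of our research study as part of the standard of care". It describes traditional treatment of contraversive pushing as "progressing functional mobility while orienting to midline with various forms of visual and tactile feedback". Eligibility requires "Unilateral, supratentorial ischemic or hemorrhagic stroke within the past six months". The protocol describes no group on usual therapy alone, no sham group and no external or historical control.

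**The concern.** A conclusion that an intervention is efficacious needs something to set the treated group against. Here each arm can be set only against the other active arm or against its own baseline. The baseline comparison takes in whatever recovery occurs within six months of stroke, and whatever usual therapy achieves. By the protocol's own account, usual therapy for this condition works on the same problem, orientation to midline.

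If both arms improve by a similar amount, the present wording allows a report that both interventions work. The same data would arise if neither added anything. Improvement in the EksoNR arm alone could likewise be presented as confirming the Background hypothesis. What is at stake is a device-efficacy claim that the data cannot support.

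**Working it through.** The protocol gives no figure to reproduce here: no effect size, standard deviation, significance level or power. The check is about what the two arms can identify.

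**Identification.** Let U be the mean change from recovery and usual therapy, and let E and T be the added effects of the EksoNR and treadmill packages.

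- Change in the EksoNR arm = U + E
- Change in the treadmill arm = U + T
- Difference = (U + E) − (U + T) = E − T

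There are two observed means and three unknowns. U cancels from the difference but not from either arm's own change. Two illustrations:

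- Both arms change by 4 points: U = 4 with E = T = 0 fits exactly as well as U = 0 with E = T = 4.
- Arm changes of 3 (treadmill) and 2 (EksoNR): for U = 0, 1, 2, 3 the implied effects T / E are 3/2, 2/1, 1/0 and 0/−1. The difference T − E is 1 every time.

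**Condition on the difference.** The cancellation needs the same U in both arms. If the groups differ at entry, the difference is (E − T) + (U_E − U_T), and the second term does not vanish. The protocol says only that a participant is placed in a group (Procedures Involved, screening and baseline procedures) and states no random allocation. A separate list, EksoNR Exclusion Criteria, adds limits on weight, height, hip width, joint range, leg-length discrepancy, anxiety and other conditions for that device. U_E = U_T is therefore not secured by anything stated.

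**Illustration of the risk.** Three things here are assumed and not taken from the protocol: efficacy is read from each arm's own change by a two-sided 5% paired t-test; the training adds nothing (E = T = 0); and the background change is d standard deviations of the change score. Group sizes are 5 and 10 (Background) and 15 (the 30 in the Study Summary, split equally). The chance that one arm shows significant improvement is P(t′ > t(0.975, n−1)), with t′ noncentral t, n−1 degrees of freedom and noncentrality d√n. The chance for both arms is its square.

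| n per arm | d | d√n | One arm | Both arms |
|---|---|---|---|---|
| 5 | 0.5 | 1.118 | 14% | 1.9% |
| 5 | 1.0 | 2.236 | 40% | 16.1% |
| 5 | 1.5 | 3.354 | 71% | 50.5% |
| 10 | 0.5 | 1.581 | 29% | 8.6% |
| 10 | 1.0 | 3.162 | 80% | 64.5% |
| 10 | 1.5 | 4.743 | 99% | 97.5% |
| 15 | 0.5 | 1.936 | 44% | 19.2% |
| 15 | 1.0 | 3.873 | 95% | 90.1% |
| 15 | 1.5 | 5.809 | >99% | 99.9% |

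With d = 0 the one-arm figure is 2.5% at every size.

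**Precision of the comparison.** The half-width of the 95% interval for the difference is t(0.975, 2n−2) × √(2/n), in SD of the change score:

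- n = 5: 2.306 × √0.4 = 1.46
- n = 10: 2.101 × √0.2 = 0.94
- n = 15: 2.048 × √0.1333 = 0.75

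An interval this wide that includes zero cannot show that the two interventions are equivalent. Even true equivalence would not show that either one works.

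**The case against.** The strongest reply is that the sentence means relative efficacy. The protocol's title calls the study a comparison, the sentence itself opens with comparing the groups, and the EksoNR hypothesis follows a sentence on traditional treatment and cites a reduced burden on clinicians, which is implicitly comparative. This softens the point but does not remove it. The sentence lists efficacy separately from the comparison, the Objectives speak of the effect of the interventions, and the hypothesis names no comparator.

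A second reply is that other analyses could reach the added effect, since step counts and time in the heart-rate zone are recorded each session, outcomes are repeated weekly, and an external control could be found. That is fair as far as it goes, so it would be wrong to say that no analysis could ever address the question. But the protocol describes no external control, and dose depends on stay: "The intervention will be delivered three times weekly up to 24 sessions or until the participant is discharged". A dose-response analysis would thus be confounded by length of stay, and probably by severity. Such analyses need assumptions that these data cannot test.

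Third, an active comparator on top of standard care is a legitimate choice for a small study. That stands. The point asks that the conclusion match the design, not that the design change.

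Two stronger readings are tempting. A reader might take the table above as the plan's false-positive rate. It is not: the protocol states no within-arm test and no background change, and its statistical analysis plan is not at hand. A reader might also infer that the between-arm difference is a clean device effect. The documents do not support that either, given the silence on random allocation and the EksoNR-only exclusions.

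**Conclusion.** The point holds in this form: conclusions on the efficacy of each intervention are a stated output that the described design does not support without untestable assumptions. This rests on the arm structure, the concurrent therapy and the time since stroke, all of which the protocol states, and not on any assumed number. It is not a detail left to an analysis plan, because the fault lies in what the protocol says it will conclude.

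The size of the resulting risk depends on the unknown background change. Under the assumptions shown, both arms would appear to improve significantly with no training effect in anything from 1.9% of trials (5 per arm, 0.5 SD) to 99.9% (15 per arm, 1.5 SD). The between-group difference is the defensible target, but it is imprecise and, as the protocol stands, possibly confounded. The correction should be made; the fault lies in the wording of the conclusion and does not invalidate the study.

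**What to change.** Replace the sentence in Data Collection and Analysis with:

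> Analysis will estimate the difference between the two groups in change in contraversive pushing, with a 95% confidence interval. Change within each group will be reported descriptively and will not be attributed to the intervention. An interval that includes zero will not be read as showing that both interventions work or are equivalent. The difference will be read as an effect of the device only if allocation is random among participants eligible for both devices, and otherwise as a possibly confounded association.

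Reword the purpose in the Objectives as a comparison of the EksoNR group with the treadmill group, and state the Background hypothesis relative to the treadmill group.

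The cost is wording in three places, with no new data, visits or participants. The downside is that the study gives up a stand-alone efficacy claim for each device and is left with an imprecise difference. If the sponsor wants that difference to carry a causal reading, allocation must be random among participants who meet both sets of criteria, and the protocol should say so.
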